Self-Reported Alcohol Use (secondary aim). Assess the effectiveness of *IPS Plus Abstinence-Contingent Wage Supplements* in reducing self-reported alcohol use during the intervention. We will use three self-report measures of alcohol use (based on TLFB) during the 30 days prior to each of the 6 monthly assessments during the year after random assignment. We will assess: 1) the percent of days abstinent from alcohol; 2) the average number of standard drinks per drinking day ingested; and 3) the percent of heavy drinking days (≥ 5 standard drinks per day for men and ≥ 4 standard drinks per day for women). Hypothesis: We expect that *IPS Plus Abstinence-Contingent Wage Supplement* participants will have less self-reported alcohol use during the intervention after random assignment relative to Usual Care Control.

Employment (secondary aim). Assess the effectiveness of *IPS Plus Abstinence-Contingent Wage Supplements* in promoting employment during the intervention. We will assess the number of days participants are employed during the 30 days prior to each of the 6 monthly assessments during the intervention after random assignment. Hypothesis: We expect that *IPS Plus Abstinence-Contingent Wage Supplements* will increase employment during the intervention after random assignment relative to Usual Care Control.

Post-Intervention Effects (secondary aim). Assess the effectiveness of IPS Plus Abstinence-Contingent Wage Supplements in promoting employment and abstinence from alcohol after the intervention ends. We will compare the groups on self-reported measures of alcohol use and employment at 6- and 12-month follow-up assessment time points after the intervention ends. Hypothesis: We expect that IPS Plus Abstinence-Contingent Wage Supplements may need to be maintained to promote long-term employment and abstinence from alcohol, and thus alcohol abstinence and employment may not be sustained after the intervention ends.

Economic Outcome Measures

Costs of Treatment (secondary aim). Assess the costs of treatment for Usual Care and IPS Plus Abstinence-Contingent Wage Supplements. We will assess the total cost per participant in both study groups. Hypothesis: We expect that treatment costs for IPS Plus Abstinence-Contingent Wage Supplements will be higher per person relative to Usual Care due to the IPS and wage supplements and because we expect that IPS Plus Abstinence-Wage Supplement participants will have greater treatment engagement.

[figure not shown]

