The primary outcome measures will be analyzed with a longitudinal binomial regression model using generalized estimating equations (GEE; Diggle & Diggle, 2002). We used Liu and Liang (Liu & Liang, 1997) to determine the total N required to detect differences between groups with 80% power. The adjacent figure shows the total number of participants (N) that would be required to detect a difference of 15% between the Usual Care Control and the IPS Plus Abstinent-Contingent Wage Supplement with the monthly assessments. The figure shows possible percentages for the Usual Care Control group because that value affects the sample size required. Fifteen percent is smaller than any difference in any Therapeutic Workplace study in which we promoted alcohol abstinence in homeless adults or cocaine abstinence in methadone patients (see figure in "Significance Section"). The horizontal red lines show the number of participants planned based on the number of participants randomized to the two groups without (top dashed red line) and after adjusting for the anticipated rates of missing data (10% missing, bottom solid red line). Based on this analysis, we need to randomize 130 participants (dashed red line) to ensure that we have sufficient sample sizes after adjusting for the rates of missing data. After adjusting for missing data (10% missing), this would yield a sample size of 117 participants (130 participants x 0.90 collected assessments = 117 participants). The adjusted sample size of 117 participants (solid red line) is a little more than the maximum number of required participants.

Main Statistical Analyses

Main analysis. All measures assessed repeatedly will be analyzed with a longitudinal binomial regression model. Within-person correlated outcomes will be handled using GEE (Zeger et al., 1988). Measures assessed once will be analyzed using logistic regression. The magnitude of effect for both

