regression and GEE will be expressed using odds ratios with 95% CI. Analyses will include all randomized participants as intent-to-treat, and will be adjusted for pre-specified covariates used for stratification (Pocock et al., 2002). Tests will be two-sided and, because we have one primary outcome, alpha will be set at 0.05. Based on our previous experience, we expect rates of attrition at monthly visits to be low. If rates are higher than expected, we will use mixed effects models rather than GEE estimation, as the former has less strict assumptions regarding missing data (MAR, rather than MCAR). If it appears that the missing data are MNAR, then we will fit pattern mixture models as described by Hedeker & Gibbons (1997).

Missing data. We expect to collect >90% of assessments. Our approach to handle missing data will be to impute all missing values as the adverse outcome (e.g., alcohol positive). Model parameter estimates from this approach will be compared to a method without imputation. If these methods yield differing results, conclusions will need to be tentative, but results from both approaches will be reported in publications. To investigate sensitivity to missing values, participants with and without missing values will be compared by covariates and treatment assignment. If rates of missingness are higher than expected, we may use multiple imputation (Rubin, 1996) or pattern mixture models (Hedeker & Gibbons, 1997) to obtain unbiased estimates of treatment effects.

Consideration Of Sex And Other Variables In Moderating The Outcomes

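### Average drinks per drinking day is assigned a binomial model and odds ratio that do not fit it, and 30-day windows without drinking have no coding rule

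*Combined protocol and SAP*

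**What the plan says.** Section 7b (Self-Reported Alcohol Use) lists three Timeline Followback (TLFB) measures for the 30 days before each of six monthly assessments: percent days abstinent, "the average number of standard drinks per drinking day ingested", and percent heavy drinking days.

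Section 7c (Main analysis) sets the model by how often a measure is taken: "All measures assessed repeatedly will be analyzed with a longitudinal binomial regression model", with generalized estimating equations (GEE) for within-person correlation, and "Measures assessed once will be analyzed using logistic regression". The size of effect for both "regression and GEE will be expressed using odds ratios with 95% CI". The same paragraph adds: "Analyses will include all randomized participants as intent-to-treat".

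Section 7c (Missing data) follows a statement that more than 90% of assessments should be collected. It says: "Our approach to handle missing data will be to impute all missing values as the adverse outcome (e.g., alcohol positive"; and then: "Model parameter estimates from this approach will be compared to a method without imputation". Multiple imputation is mentioned only as an option if missingness is higher than expected.

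No section gives another model, a cut-point or a transformation for drinks per drinking day, or says how to code a completed window with no drinking days.

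**The concern.** There are two gaps, and both concern the same measure.

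First, the model. A binomial model with an odds ratio needs a yes/no outcome or a count of events out of a known number of trials. Drinks per drinking day is total drinks divided by drinking days. It has no trials denominator and is normally 1 or more.

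Second, the measure does not exist in a window without drinking. Such windows are what the trial is trying to produce: Section 4a ties the full wage supplement to alcohol-negative readings, and Section 7a hypothesises more abstinence in the IPS arm. They can therefore be expected to occur unequally between arms. Excluding them selects on drinking after randomization and conflicts with analysing everyone randomized. Scoring them zero keeps everyone but changes the quantity measured.

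At stake is one named secondary result, whose model and coding would have to be chosen later, possibly after data are seen.

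**Working it through.** **The plan's own figure.** Section 7c (Power Analysis): 130 × 0.90 = 117. It reproduces and is not in dispute.

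**Fit of each repeated measure to a binomial model.**

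| Measure (Section 7b) | Form | Binomial possible? |
|---|---|---|
| Percent days abstinent | days out of 30 | yes |
| Percent heavy drinking days | days out of 30 | yes |
| Days employed | days out of 30 | yes |
| Drinks per drinking day | total drinks / drinking days | no; 0/0 if there are no drinking days |

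**How far the coding can move the result.** The documents give no inputs, so all of these are assumed:
- a = share of control windows with no drinking: 0.05 to 0.60.
- d = additional share in the IPS arm: 0.05 to 0.15.
- r = drinks per drinking day of those whom the intervention makes abstinent, relative to the remaining drinkers (mean set to 1): 0.5, 1 or 1.5.
- k = factor by which the intervention changes intensity among those still drinking. The base case is k = 1, no change.

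The control mean among windows with drinking is [(1−a−d) + d·r]/(1−a), and the IPS mean is k. So the IPS/control ratio is:
- no-drinking windows excluded: k(1−a) / [(1−a−d) + d·r]
- no-drinking windows scored zero: k(1−a−d) / [(1−a−d) + d·r]

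For fixed r and k, both depend only on d/(1−a), so the extremes lie at (a = 0.05, d = 0.05) and (a = 0.60, d = 0.15). With k = 1:

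| r | Excluded | Scored zero |
|---|---|---|
| 0.5 | 0.95/0.925 = 1.03 to 0.40/0.325 = 1.23 | 0.25/0.325 = 0.77 to 0.90/0.925 = 0.97 |
| 1 | 1.00 throughout | 0.25/0.40 = 0.63 to 0.90/0.95 = 0.95 |
| 1.5 | 0.40/0.475 = 0.84 to 0.95/0.975 = 0.97 | 0.25/0.475 = 0.53 to 0.90/0.975 = 0.92 |

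In a middle case (a = 0.40, d = 0.10), excluding gives 1.09, 1.00 and 0.92 for the three values of r. Scoring zero gives 0.91, 0.83 and 0.77.

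**Dependence on k.** Both ratios scale with k. For r = 0.5:
- k = 0.8: the excluded range becomes 0.82 to 0.98.
- k = 1.2: the scored-zero range becomes 0.92 to 1.17.

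**Windows affected.** With an equal split (assumed; the ratio is not stated), 65 × 6 = 390 windows are planned per arm. With the plan's 10% missing, 390 × 0.90 = 351 are collected. Excluding no-drinking windows drops 0.05 × 351 ≈ 18 to 0.60 × 351 ≈ 211 control windows.

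**The case against.** **Can the text be read so that it works?** Three readings were tried:
- Dichotomising the measure needs a cut-point. The 5- and 4-drink thresholds define heavy drinking days only.
- Reading binomial as negative binomial does not agree with reporting odds ratios.
- The mixed-model fallback in Section 7c is triggered by attrition and names no distribution.

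**Does it matter much?** This is one of three self-report measures under one secondary aim. Percent days abstinent has a fitting model on the same TLFB windows and keeps the abstinence information that excluding no-drinking windows would lose. This stands and limits the weight of the point.

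**Is the direction established?** A reader might infer that excluding no-drinking windows would show harm, or that scoring zero always shows benefit. The documents support neither. Both patterns depend on k and r, for which the plan gives no values, and Section 7b hypothesises less drinking in the IPS arm. At k = 0.8 every excluded ratio in the table falls below 1; at k = 1.2 some scored-zero ratios exceed 1. No standard errors were calculated, so ratios near 1 may not be distinguishable from 1.

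**Would abstinent windows be scored as adverse?** A reader might also infer this from the missing-data rule. It is not the natural reading, because that rule concerns assessments that were not collected and a completed abstinent window was collected. For the same reason, the planned comparison without imputation does not settle how to code such windows.

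**Conclusion.** The concern holds for one secondary measure. The stated model and odds ratio cannot be applied to average drinks per drinking day, and the measure has no rule for completed windows without drinking. This follows from the text alone and needs no assumption.

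The numerical ranges show only that the result can depend on the coding. They rest on the assumed a, d and r and on unchanged intensity among remaining drinkers, and they do not forecast a sign.

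It would be wrong to extend the point to the primary outcome, alpha, the sample size or the day-count measures; none is affected. At the 6- and 12-month follow-ups the gap arises only if this measure is used there. Section 7b (Post-Intervention Effects) refers to self-reported alcohol measures without saying which.

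The plan should be amended on this measure, but the main conclusion of the trial does not depend on it.

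**What to change.** By a short dated amendment to Section 7c:

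1. Limit the binomial GEE and odds ratio to measures that are days out of the window.
2. Analyse drinks per drinking day, in windows with drinking, by a log-link GEE: for example, total drinks with log drinking days as offset, a stated working variance such as Poisson, and robust standard errors. Report a ratio of means, labelled as conditional on drinking and not a randomized comparison.
3. State that completed windows without drinking are observed, not missing.
4. Give the comparison of all randomized participants as mean drinks per calendar day over the TLFB window, zero when abstinent, with the same log-link model.
5. For uncollected windows, the adverse-outcome rule has no numeric value for this measure. Specify multiple imputation, reported alongside the analysis without imputation.
6. Use the same rules at the 6- and 12-month follow-ups if the measure is used there.

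No new data are needed, because TLFB is already collected, and the named measure is kept. The cost is slightly more analysis and a conditional estimate that cannot alone support a treatment claim. If outcome data have already been seen, the choice must be labelled post hoc.

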To increase the chance that we engage participants, upon enrollment, participants will be invited to participate in a 1-week Therapeutic Workplace induction period. During the induction period, participants will be asked to maintain contact with Therapeutic Workplace staff by calling or texting staff every weekday. We have used similar induction procedures in our prior studies to successfully engage participants. Participants will be able to earn \$20 per weekday for maintaining contact with our staff during the induction period. Participants who complete the 1-week induction will be given a wearable alcohol biosensor, invited to call in to the Therapeutic Workplace every weekday for 3 weeks, and can earn about \$32/weekday for participating in our job-skills training program. Participants will be taught about the Therapeutic Workplace. Some or all of the training may be given through a computer-based training program. We may also evaluate the effectiveness of the training program by giving participants tests before and after they complete parts or all of the training program. We may re-administer the test at the end of the intervention to measure retention. Each Therapeutic Workplace participant will have a participant ID, which will be used to enter participant drug and alcohol testing results into our therapeutic workplace software, automatically implement any responses to drug and/or alcohol use based on testing results, and to automatically calculate participant daily pay based on compliance with drug and/or alcohol contingencies. Participants will be required to wear their wearable alcohol biosensor (SCRAM or BACtrack Skyn), which will record transdermal alcohol concentrations. Participants will be given separate care and use information about their wearable alcohol biosensor. Participants who wear a SCRAM bracelet will need to come to the Therapeutic Workplace (about every 30 days) so that the data stored on their bracelet can be transmitted to SCRAM_{NET} and accessed by our research staff. Participants who wear a BACtrack Skyn bracelet will need to transmit the data stored on their bracelet via Bluetooth using a smartphone. At the end of Phase 1, participants will be randomly assigned to groups.

Experimental Design

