Participants (N = 130) will be randomly assigned to a Usual Care Control or IPS Plus Abstinence-Contingent Wage Supplements group. Computerized urn randomization (Wei & Lachin, 1988) will balance groups on characteristics that may influence outcome: (1) percent of days abstinent from alcohol (assessed by transdermal alcohol concentrations prior to random assignment; \geq rolling median, Y/N); (2) evidence of opiate and cocaine use from the assessment prior to random assignment (Y/N); (3) completed high school or obtained a GED (Y/N); and (4) gender (male/female). Participants will be stratified by alcohol and drug use because they should predict alcohol abstinence during the intervention period. High school completion or GED should be associated with employment. Participants will be stratified by gender to balance the two groups on a key biological factor that may influence outcome.

Individual Placement and Support (IPS) & Abstinence-Contingent Wage Supplement Group

This group will receive the full intervention being evaluated in this study for 6 months.

Individual Placement and Support (IPS). After Phase 1, participants will be offered the IPS model of supported employment for 6 months. IPS involves rapid job search, promotes competitive employment, and provides job supports and benefits counseling.

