Participants will be removed from the study if they threaten the safety of CLH staff or other research participants, or of any other persons on the Johns Hopkins Bayview Campus.

g. Description of what happens to participants receiving therapy when study ends or if a participant's participation in the study ends prematurely.

Throughout the study, participants will be given referrals to services they might need (e.g., drug counseling, housing, medical, or employment services).

5. Inclusion/Exclusion Criteria

Inclusion criteria: a) 18 to 55 years old; b) homeless at the time of intake as defined by the McKinney-Vento Homeless Assistance Act (lacked a fixed, regular, and adequate nighttime residence including staying in a shelter, on the street, in an abandoned house or building, a car, or a park); c) unemployed; d) meet DSM V criteria for alcohol use disorder; and e) interested in obtaining employment. Exclusion criteria: a) report current suicidal/homicidal ideation; b) currently have nickel or other metal allergies, deep vein thrombosis, or leg ulcers where the SCRAM bracelet should be placed. Individuals excluded from the study will be linked with appropriate care as needed.

6. Drugs/ Substances/ Devices

NA a. The rationale for choosing the drug and dose or for choosing the device to be used.

NA b. Justification and safety information if FDA approved drugs will be administered for non-FDA approved indications or if doses or routes of administration or participant populations are changed.

NA c. Justification and safety information if non-FDA approved drugs without an IND will be administered.

NA

7. Study Statistics

a. Primary outcome variable.

Biologically-Verified Alcohol Abstinence (primary aim). Assess the effectiveness of *IPS Plus Abstinence-Contingent Wage Supplements* in promoting biologically-verified alcohol abstinence during the intervention. We will assess the number of days of alcohol abstinence (based on transdermal alcohol concentrations) during the 6 months after random assignment. Primary Hypothesis: Our primary hypothesis is that *IPS Plus Abstinence-Contingent Wage Supplements* will promote alcohol abstinence during the intervention after random assignment relative to Usual Care Control.

b. Secondary outcome variables.

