We will conduct analyses to identify biological and other variables that moderate the outcomes of employment and alcohol abstinence. We will examine efficacy differences as a function of four variables assessed prior to random assignment by including interaction terms in our regression models: 1) Percent of days abstinent from alcohol (based on transdermal alcohol concentrations) prior to random assignment. 2) Opiate- and cocaine-negative urine samples from the assessment prior to random assignment. 3) Completed high school or obtained a GED; and 4) gender (male/female). Alcohol use and opiate/cocaine use prior to random assignment should be associated with higher rates of alcohol use and lower rates of employment during the 6 months after random assignment. We expect that high school completion or obtaining a GED will be associated with higher rates of employment. Gender is a key biological factor that may influence outcome. We also expect that the effect of IPS Plus Abstinence-Contingent Wage Supplements will be affected by these variables.

Balancing of potential moderators of treatment response via urn randomization merely ensures that the estimation of the treatment effect is unbiased. Balancing the randomization by these variables allows for them to be adjusted for in subsequent analyses. It does not take the place of these adjustments. Moderator analysis entails fitting a model with the main effects of treatment and the putative moderating variable, and their interaction. Likewise, balancing the variables during randomization does not take the place of fitting this interaction. For more discussion, see Pocock et al. (2002).

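### Adding baseline percent days abstinent to the primary GEE, beside the rolling-median Y/N flag, would be a cheap precision step with a small, conditional gain in power

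*Combined protocol and SAP*

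**What the plan says.** Section 7c, Main analysis, fits a longitudinal binomial regression by GEE, reports odds ratios with 95% intervals, tests two-sided at 0.05, and states that analyses "will be adjusted for pre-specified covariates used for stratification". It does not say how each covariate is coded.

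Section 4a, Experimental Design, lists four urn factors. The first is percent of days abstinent by transdermal readings before randomization, dichotomized at or above the "rolling median, Y/N". The reason given is: "Participants will be stratified by alcohol and drug use because they should predict alcohol abstinence during the intervention period".

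The baseline window is short. After a one-week induction, participants are "given a wearable alcohol biosensor, invited to call in to the Therapeutic Workplace every weekday for 3 weeks" (section 4a, Therapeutic Workplace and Job-Skills Training). The primary outcome in section 7a counts abstinent days from the same kind of reading over the 6 months after randomization.

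Section 7c, on sex and other moderators, names the variable without a cut-off: "Percent of days abstinent from alcohol (based on transdermal alcohol concentrations) prior to random assignment". It then says: "Balancing the randomization by these variables allows for them to be adjusted for in subsequent analyses".

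The Power Analysis uses a published GEE method "to determine the total N required to detect differences between groups with 80% power" and describes no covariate adjustment.

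**The concern.** A median split puts a participant just above the cut together with one who never drank, and a participant just below it with one who drank daily. The plan expects this factor to predict the primary outcome. If the relation is graded, the split gives up part of what the covariate could explain. The percentage must be computed anyway to form the flag, so using it needs no new data.

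What is at stake is a little power for the single primary comparison. There is also a small matter of pre-specification: the effect measure is a conditional odds ratio, which moves slightly with the form of the covariate, so the form should not be left to the analyst.

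**Working it through.** **The plan's own figure.** 130 x 0.90 = 117, which reproduces exactly. The required N behind it can be approximated by N = 2(z_a + z_b)^2 [p0q0 + p1q1][1 + (m-1)rho] / (m d^2), with m = 6 assessments and d = 0.15. Taking p0 = 0.425 and p1 = 0.575 (an assumption that places the rates around 50%), N = 56.83 x (1 + 5 rho). This is 113.7 at rho = 0.20 and 116.5 at rho = 0.21. The text gives no rho. A value near 0.2 agrees with 117 being slightly above the maximum required. No covariate enters this formula, so any adjustment adds to the planned power.

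**Closed-form guide.** For a normal covariate, linearly related to a continuous outcome, a median split keeps 2/pi = 0.637 of R-squared. The variance ratio, percentage over flag, is (1 - r^2)/(1 - 0.637 r^2): 0.965 at r = 0.3, 0.892 at r = 0.5 and 0.830 at r = 0.6. If 80% is the unadjusted power, then power = Phi(2.80/sqrt(1 - R^2) - 1.96). Flag to percentage, this gives 82.3% to 83.6%, 86.3% to 89.9%, and 89.1% to 93.8%. It is only a guide, because the outcome is binary and the relation may not be linear.

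**Simulation of the planned type of model.** There were 20,000 trials per setting.
- From the documents: N = 130, urn randomization on four factors, rolling-median flag, 15-point difference, two-sided 0.05.
- Assumed: 21 baseline days, 180 daily outcomes, control rate 45%, person-level SD 1.93 on the logit scale, and the values of r, the shape and the share at 100% abstinent.
- Analysis: logistic GEE with robust standard errors.

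| Relation assumed | r | Flag | Percentage | Both | Both minus flag (points) |
|---|---|---|---|---|---|
| None | 0 | 0.779 | 0.778 | 0.775 | -0.4 |
| Graded | 0.31 | 0.806 | 0.817 | 0.815 | +0.9 |
| Graded | 0.45 | 0.831 | 0.857 | 0.855 | +2.4 |
| Graded | 0.62 | 0.894 | 0.937 | 0.935 | about +4 |
| Graded, 42% at 100% abstinent | 0.30 | 0.811 | 0.818 | 0.817 | +0.6 |
| Graded, 42% at 100% abstinent | 0.44 | 0.842 | 0.856 | 0.859 | +1.7 |
| Graded, 42% at 100% abstinent | 0.61 | 0.913 | 0.936 | 0.942 | +2.9 |
| Threshold, no ceiling | 0.33 | 0.813 | 0.816 | 0.815 | +0.2 |
| Threshold, no ceiling | 0.51 | 0.858 | 0.869 | 0.872 | +1.4 |
| Threshold, 33% at 100% abstinent | 0.26 | 0.807 | 0.798 | 0.806 | -0.1 |
| Threshold, 33% at 100% abstinent | 0.33 | 0.831 | 0.817 | 0.831 | 0.0 |

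The standard error of a paired power difference is 0.1 to 0.2 points. A smaller repeat (4,000 trials per setting), flag against both, gave 0.818/0.825 at r = 0.31, 0.845/0.864 at 0.45, 0.893/0.934 at 0.61, 0.835/0.838 under a threshold with a ceiling, and 0.770/0.768 at r = 0.

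**Six monthly outcomes, N = 117.** With intraclass correlation about 0.18, flag to both was 84.9% to 86.2% (r = 0.33), 90.0% to 92.8% (r = 0.54) and 93.2% to 97.3% (r = 0.68). With intraclass correlation about 0.39 and r = 0.66 it was 80.0% to 87.2%, so stronger within-person clustering can enlarge the gain.

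**Where the gain comes from.** At r = 0.45 the mean log odds ratio rises from 0.649 to 0.668, a factor of 1.029 (odds ratio 1.91 to 1.95). The variance ratio, flag over both, is 1.01, a factor of 1.005 on the standard error. Power 0.831 corresponds to a mean z of 1.96 + 0.958 = 2.918. Then 2.918 x 1.029 x 1.005 = 3.018, and Phi(3.018 - 1.96) = 0.855, which matches the table. At r = 0.62 the two factors are 0.728/0.690 = 1.055 and sqrt(1.05) = 1.025. In both cases the larger part is the shift in the odds ratio.

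**Validity.** Simulated type I error for flag / percentage / both was 0.049/0.050/0.051 (graded, r = 0.45), 0.049/0.049/0.050 (graded, r = 0.61) and 0.048/0.048/0.048 (threshold with ceiling).

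**The case against.** The strongest objection is that the plan contains no error. Adjusting for the factor as randomized is a standard, valid choice and already goes beyond what the power calculation assumed. That stands, and it sets the weight of this point.

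A second objection is that the moderator section writes the variable as a percentage and says balanced variables can then be adjusted for, so the percentage may already be intended. That reading is possible. But that section describes separate interaction models, while the main analysis points to the covariates as used for stratification. If the percentage was meant, a clarifying sentence is enough, and the further gain from carrying both terms is small: percentage and both differ by at most 0.6 points in the graded settings.

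A third objection is that the gain is not assured. Under a threshold with a ceiling it is nil, and a ceiling is plausible because section 4a, Standard Treatment Services, describes participants as detoxified or referred for detoxification. This also stands, and it is why the percentage should be added and not substituted: in the threshold-with-ceiling settings, replacing the flag loses 0.9 to 1.4 points.

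A reader might infer more than the documents support:
- **That the primary analysis is biased or underpowered.** The type I results and the unadjusted power calculation do not support that.
- **That the undefined handling of unworn baseline days is part of this point.** How unworn days count matters equally for the primary outcome, and the gain is similar under either rule tried, so it is a separate question.
- **That the same gain carries over to the self-reported alcohol outcomes.** Nothing was computed for them.

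**Conclusion.** The point holds as a minor, optional improvement in efficiency and pre-specification. On the natural reading, the primary model uses a two-level form of a baseline measure that the plan itself expects to be predictive, and the percentage is available at no cost.

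Under a graded relation, the gain in the daily-outcome simulation is about 0.6 to 0.9 power points at r near 0.3, about 2 at r near 0.45 and about 3 to 4 at r near 0.6, possibly more with stronger clustering. It is about zero (-0.1 to +1.4) under a threshold, and about 0.4 points are lost if the baseline measure is unrelated to outcome. All of this rests on assumed values of r, shape, ceiling and clustering, none of which the text gives. The interval on the log odds ratio hardly narrows until r is about 0.6.

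**What to change.** Leave the urn randomization as it is. State in the SAP that baseline percent days abstinent by biosensor enters the primary GEE as one continuous linear term, in addition to the stratification flag and the other three factors, and that the flag-only model is reported as a sensitivity analysis. Settle this before any comparison by arm. That is a workable deadline here, because section 4c marks blinding as not applicable and staff can see biosensor data.

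The cost is a sentence or two and one extra model parameter, with no new data and no design change. The conditional odds ratio shifts slightly (simulated 1.89 to 1.90 at r = 0.31, 1.91 to 1.95 at r = 0.45, 1.99 to 2.07 at r = 0.62), which is the reason to fix the form in advance and show the flag-only result beside it.
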